- Sham electroacustimulation (control) will not have stimulation

Study Population:

Inclusion criteria:

Subjects must fulfill all of the following inclusion criteria to be eligible for participation in the study:

- 1) Patients 0-18 years of age undergoing procedures on their congenital heart defects.
Additionally, patients with coarctation of the aorta for repair will be considered as a separate group and eligible for enrollment.
- 2) Willing to provide written Assent/Consent in English.

Exclusion criteria:

Subjects will be excluded if they fulfill any of the following exclusion criteria:

- 1) Patients with skin lesion over more than 50% of acupuncture sites.
- 2) Patients in renal failure.
- 3) Patients on chronic opioid therapy.
- 4) Unwilling to provide written Assent/Consent in English.

Concomitant Treatment:

All subjects will receive a standard anesthetic of propofol, remifentanyl and dexmedetomidine at doses needed to maintain a stable BIS number and lack of movement. When possible neuromuscular blocking agents will not be used. A morphine infusion will be used for postoperative pain control based on need. Those allergic to morphine will receive a substitute opiate by continuous infusion.

Study Procedures:

Screening:

Review of consent form- Subjects that provide written assent/consent and meet all inclusion and no exclusion criteria will be included into the study. Subjects may withdraw consent to participate at any time. Participation in the study is voluntary. Adverse events will be recorded after informed assent/consent obtained.

Surgery: Treatment/Sham

Eligible subjects will undergo blood sampling (3.5cc) and urine sample (0.5-2cc) will be obtained prior to stimulation/sham.

All subjects will have electroacustimulation pads applied at four points bilaterally: pericardial 4 (PC 4), pericardial 6 (PC 6), large intestine 4 (LI 4) and stomach 36 (ST 36). No needles will be used. ([Appendix A; 1](#))

Subjects will be randomized. Randomization will be done using block randomization with block sizes between 4 and 8. The sham procedure will use the identical set up as the treatment group, but those participants in the sham group will not receive the electro-stimulation. Stimulation/sham will begin as soon as possible after induction of anesthesia and obtaining baseline laboratory samples of urine and blood.

Group 1: Receive electroacustimulation (treatment) frequency will be at 2Hz and 100 Hz the amplitude will be 1000mA.

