Detailed descriptions of the variables are given in Appendix B. The information collected for each patient will include the following variables. *Outcomes:* Pain score; inotropic score; Narcotic use; renal laboratory values: creatinine, neutrophil gelatinase-associated lipocalin (NGAL), WNT4, AKIN score; superoxide dismutase; indicator for pneumonia; time-to-extubation (intubation time, extubation time); length of pediatric intensive care unit (PICU) stay (arrival time, discharge time). *Other variables:* Age, sex, cardiac defect, cyanosis, RACHS score, cardiopulmonary bypass time (CPB), cross clamp time and surgery start and end time, occurrence of nausea, vomiting event, urine output, number of lobes with atelectasis.

Analytic methodology

Randomization: Eligible participants will be randomized to the acupuncture treatment or control group using a randomly varying block randomization method to ensure equal distribution among treatment groups.²² The project statistician, who will have no contact with the participants or any of the personnel assessing the patients, will generate a randomized assignment master list and provide this information only the study personnel who will be setting up the acupuncture device. Each participant will be assigned a unique number that will follow the patient through the study. The study number and participant's name will be retained on a secure electronic database; this information will be linked to the randomization assignment to create a crosswalk file. It will be stored in a separate password-protected database. At the end of the study, the cross-walk file will be used to link the patient data and treatment allocation.

Sample size:

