To address the overall difference between the control and the acupuncture group, we will look at the score changes between baseline and 48 hours. For the continuous outcomes, a t-test based on the difference in outcome will be used to compare the two treatment groups. For the categorical outcomes, a logistic regression model (generalized linear model with binary or multinomial outcome) will be used to compare the two treatment groups' at baseline and 48 hours. The generalized linear hypothesis methodology will be used to contrast the two time points. This approach will provide consistency of modeling methodology for the secondary analyses. Adjusted models will be considered (e.g. glm regression with identity and/or logit links) to account for any data imbalances, potential confounders, etc. Minimally, a RACHS score adjustment will be assessed for its relevance.

A secondary analysis will be used to describe the longitudinal (repeated measures) outcome trends. A generalized linear mixed-effects regression model will be used for longitudinal data. Both unadjusted and adjusted trends will be assessed. We will account for both heteroscedasticity and autocorrelation variance-covariance structures. The generalized linear model approach will permit trend characterizations for either continuous or categorical outcomes under the same generalized linear model framework.

[figure not shown]
All results, predicated on formal hypothesis testing methodology, will use an alpha-level of 0.05 for statistical significance. Bonferroni or Scheffe adjustments will be used, when appropriate, to retain the family-wise alpha level of 0.05 when performing multiple tests under the same global hypothesis or construct. Every effort will be used to ensure all relevant information is collected. In the event of missing data, generalized estimating equations for longitudinal analysis will be used. All statistical analysis will be done using the most recent version of the R language for statistical computing and graphics.

Tentative time table: Approximately 2 years to enroll 108 subjects.

[figure not shown]
References:

- 1) Instruction manual for KWD-808I Multipurpose health device, Ying Di page 21.
http://www.ib3health.com/products/Acupunctoscope/KWD808_I.asp#808I_Instruct [Accessed Sept. 5, 2016]

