1. AVR

2. Ross procedure

3. LVOT patch

4. Ventriculomyotomy

5. Aortoplasty

6. Mitral valvuloplasty or replacement

7. Tricuspid valvuloplasty or valvectomy or replacement

8. Tricuspid valve repositioning (Ebstein's) (> 30 days of age)

9. Anomalous coronary artery repair with or without intrapulmonary tunnel (Takeuchi)

10. Closure of semilunar valve (aortic or pulmonary valve)

11. RV-PA conduit

12. LV-PA conduit

13. DORV repair with or without RV obstruction

14. Fontan

15. AVSD (complete or transitional) repair with or without valve replacement

16. PA banding

17. Tetralogy with Pulm. Atresia repair

18. Cor triatriatum repair
19. Systemic-Pulmonary artery shunt
20. Atrial switch operation
21. Arterial switch operation
22. Pulmonary artery reimplantation
23. Annuloplasty
24. Coarctation & VSD repair
25. Cardiac tumor excision

RACHS category 4:

1. Aortic valvuloplasty (;;; 30 days of age)
2. Konno procedure
3. Complex defect (Single ventricle) repair with VSD enlargement
4. TAPVR repair (;;; 30 days of age)
5. Rastelli procedure
6. Atrial switch with VSD closure
7. Atrial switch with subpulmonary stenosis repair
8. Arterial switch with PA band removal
9. Arterial switch with VSD closure
10. Arterial switch with subpulmonary stenosis repair
11. Truncus repair
12. Repair of ... or interrupted aortic arch with or without VSD repair
13. Unifocalization ... Tetralogy-PA
14. ...

RACHS category 5:

1. Tricuspid valve repositioning for neonatal Ebstein's (:S 30 days of age)
2. Truncus with Interrupted aortic arch repair

RACHS category 6:

1. Norwood operation
2. ...

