Appendix B: Variable descriptions.

Variable	Description	Measurement times	Measurement scale
Outcomes			
Pain score	Age appropriate WVUH approved Nurse guided pain scoring. The pain scale score will be recorded in the electronic medical record.	Every 2 hours for 48 hours	Tool: NIPS score, FLACC score or Visual analog scale Scale: 0-10; 0=none, 10=worst pain
Inotropic score	IS or VIS 1 st 24 hours IS or VIS 24-48 hours	Every 6 hours for the first 48 hours of observation	Group 1-5
Narcotic use	Opiate use will be its own variable as well as a surrogate for pain as comfort will be maintained at a score less than 40% of the max possible score for the pain scoring system used.	Every 2 hours for 48 hours	mcg/kg/hr
Creatinine/Urine	Assessment of AKI-renal complication	Baseline, 6, 12, 24, and 48 hrs post CPB	Creatinine mg/dl Urine ml/kg/hr
Neutrophil gelatinase-associated lipocalin (NGAL)	Renal biomarker-urine sample collected and frozen-renal complication	Baseline, 6, 12, 24, and 48 hrs post CPB	ELIZA
WNT4	Renal Biomarker-urine sample collected and frozen-renal complication	Baseline, 6, 12, 24, and 48 hrs post CPB	ELIZA
AKIN score	Acute kidney injury (AKI)-renal complication	Every 6 hours for the first 48 hours of observation (EMR)	Stage 1-3
Superoxide dismutase	Renal Biomarker-urine sample collected and frozen-cardiac injury-complication	Baseline, 6, 12, 24, and 48 hrs post CPB	ELIZA
Pneumonia	complication	Daily (Chest x-ray)	Indicator: 0=No, 1=Yes
Intubation time	The date and time of intubation as part of surgery prep.	Obtained from patient's EMR	Date and time
Extubation time	The date and time of extubation as part of surgery prep.	Obtained from patient's EMR	Date and time
PICU arrival	The date and time of arrival in the PICU	Obtained from patient's EMR	Date and time
PICU discharge	The date and time of discharge from the PICU	Obtained from patient's EMR	Date and time
Other variables			
Age	Age of the patient	Baseline	In days
Sex	Sex of the patient	Baseline	Indicator: 0=Male, 1=Female
Cardiac defect	Type of CD	Baseline	Diagnosis

Cyanosis	Blueness of skin- based on room air oxygen level less than 90% sat-guide for opiate amount-complication	Baseline	1=yes 2=no
RACHS score	Randomization Guide	Baseline	Categorical: 1 through 6
CPB start time/ Aortic clamp time	Cardiopulmonary bypass (CPB) start time/ Placement of aortic clamp	Obtained from patient's EMR	Date and time

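### The plan does not settle whether RACHS guides allocation and leaves RACHS adjustment optional; RACHS should be a prespecified term in every between-arm comparison

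*Combined protocol and SAP*

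**What the plan says.** Appendix B, under Other variables, lists the RACHS score as a baseline categorical variable with six levels and describes it as "Randomization Guide".

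Randomisation is described in three places. Treatment Groups (in the Research Plan) and Surgery: Treatment/Sham (in Study Procedures) carry the same sentence: "Randomization will be done using block randomization with block sizes between 4 and 8". Analytic methodology, Randomization, says that participants are allocated "using a randomly varying block randomization method to ensure equal distribution among treatment groups" and that the project statistician "will generate a randomized assignment master list". None of the three mentions RACHS, a stratum or minimisation.

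The Statistical analysis plan compares continuous outcomes by a t-test on the change in outcome, and categorical outcomes by logistic regression. It then allows adjusted models to deal with imbalance or confounding, and ends: "Minimally, a RACHS score adjustment will be assessed for its relevance".

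Eligibility sets no severity limit: "Patients 0-18 years of age undergoing procedures on their congenital heart defects". Coarctation is mentioned apart ("patients with coarctation of the aorta for repair will be considered as a separate group and eligible for enrollment"), but no separate randomisation is described for it. The RACHS list in Appendix A.6 runs from secundum ASD in category 1 to the "Norwood operation" in category 6.

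**The concern.** A statistician building the allocation list from the randomisation text would produce one blocked sequence. One who took the Appendix B label at its word would produce blocks within RACHS levels. The two schemes have different properties and call for different analyses, and the plan does not say which applies.

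RACHS grades the complexity of the operation, which plausibly bears on troponin, inotropic support, kidney injury and time to extubation. Taking change from baseline does not remove this, because the baseline troponin is drawn before the operation whose complexity differs between children. If allocation ignores RACHS, a chance difference in case mix enters the unadjusted comparison. If allocation uses RACHS, an unadjusted test ignores the stratifier and its standard error is too large. In both cases, deciding on adjustment after seeing whether it is relevant leaves the choice of model to the data.

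**Working it through.** **Inputs from the documents.** 108 children, 54 per arm; two-sided alpha 0.05; power 80%; morphine-equivalent dose 0.71 versus 0.57 mg/kg (difference 0.14); SDs 0.3 and 0.2 (all from Sample size); block sizes between 4 and 8.

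**Assumed, because the documents give neither.** The share of children in RACHS 3-6 (10% to 50%), and the share of outcome variance that RACHS explains, R² (10% to 30%).

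**1. The plan's sample size reproduces.** n per arm = (1.96 + 0.84)² × (0.3² + 0.2²) / 0.14² ≈ 52.06, rounded up to 53. With the noncentral t for the unequal-variance test, power is 79.9% at 53 per arm and 80.6% at 54. So 54 is the smallest number that reaches 80%, and nothing below changes it.

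**2. Chance imbalance.** 10,000 simulated trials per row, 108 children, block sizes drawn from 4, 6 and 8:

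| Assumed share in RACHS 3-6 | One list: gap ≥10 points | One list: gap ≥15 points | One list: 95th percentile of gap | Two RACHS strata: 95th percentile of gap |
|---|---|---|---|---|
| 10% | 8.2% | 1.0% | 11.1 points | 3.5 points |
| 20% | 18.9% | 4.0% | 14.8 points | 3.2 points |
| 30% | 25.1% | 7.7% | 16.7 points | 2.9 points |
| 50% | 28.4% | 10.3% | 18.5 points | 2.2 points |

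With two strata, no gap of 10 points or more occurred. As a hand check, the SD of the gap under one list is √[p(1−p) × 2/54]: 5.8 points at p = 0.1 and 9.6 at p = 0.5. Multiplying by 1.96 gives 11.3 and 18.9 points, in line with the simulated 95th percentiles.

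**3. What a 10-point gap does to the unadjusted difference.** In SD units the shift is 0.10 × √[R² / (p(1−p))].
- At p = 0.30 to 0.45 it runs from 0.10 × √(0.10/0.2475) = 0.06 to 0.10 × √(0.30/0.21) = 0.12.
- The standard error is √(2/54) = 0.192 SD, so this is 0.33 to 0.62 of a standard error.
- The design effect is 0.14/√0.065 = 0.14/0.255 = 0.55 SD, so it is 12% to 22% of that effect.
- At p = 0.10 a gap of this size is rarer (8.2%) but moves the result more: 0.10 × √(0.10/0.09) = 0.11 to 0.10 × √(0.30/0.09) = 0.18 SD.

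**4. RACHS stratified but left out of the analysis.** True type I error = 2Φ(−1.96/√(1−R²)). For R² = 0.1, 0.2 and 0.3 this is 3.9%, 2.8% and 1.9%.

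**5. RACHS kept in the model.** Power = Φ(2.80/√(1−R²) − 1.96). For the same R² values, a nominal 80% becomes 84%, 88% and 92%.

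**6. Does step 5 need stratified lists?** With a fixed two-level RACHS term, an unstratified list inflates the variance by 1/(1−r²), where r is the chance correlation between arm and RACHS. The mean of r² is about 1/107, or about 1%. At the 95th percentile, r² = 3.84/107 = 0.036, so the inflation is 3.7%. Putting the average 1% into step 5: Φ(2.80/√(0.9 × 1.01) − 1.96) = 83.6% instead of 83.9%, and Φ(2.80/√(0.7 × 1.01) − 1.96) = 91.5% instead of 91.7%. The gain comes from adjustment, not from a second list.

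**The case against.** The strongest reply is that there is no contradiction. Permuted blocks of 4 to 8 run within RACHS strata would satisfy the randomisation text and Appendix B together, and a master list can hold stratified sequences. The documents nowhere say that the list is unstratified. This stands: the defect is an unspecified detail, resting on a two-word table entry.

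A reader might also infer that severity will be unbalanced and the result biased. The documents do not support that. Unstratified randomisation balances severity in expectation, and chance imbalance is already covered by the 5% error rate of a valid test. Nor does Appendix A.6 show that the trial will enrol the full range. It is a classification list; eligibility excludes no category, but no case mix is stated.

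The plan also anticipates the problem in part. It allows adjusted models where there is imbalance and names RACHS as the minimum covariate to assess. That lessens the concern but does not remove it, because the adjustment is conditional and no rule for relevance is given.

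Finally, the size is open to challenge. Case mix and R² are assumed, a 10-point gap usually moves the estimate by well under one standard error, and the 80% power figure belongs to morphine-equivalent dose, for which no RACHS effect is documented. These limits stand. They leave the direction unchanged: RACHS adjustment costs almost nothing if RACHS is unrelated to an outcome and helps if it is related.

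**Conclusion.** The point holds as a gap in specification with a cheap gain in precision. The documents leave open whether RACHS guides allocation, and under either reading the analysis wording is too loose.

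- **RACHS not a stratifier:** the arms differ by 10 or more points in the RACHS 3-6 share in about 8% to 28% of trials, for an assumed share of 10% to 50%. The cost is precision; the test stays valid.
- **RACHS a stratifier but omitted:** the test is conservative, with type I error of 3.9% to 1.9% for an assumed R² of 10% to 30%. There is no excess of false positives, only lost power.
- **RACHS a fixed term:** nominal 80% power becomes about 84% to 92% under the same R², whichever randomisation is used.

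The type I error and power figures apply to continuous outcomes and to whatever R² RACHS has for the outcome in question. The stronger conclusions, that the two sections cannot both be followed or that the trial needs stratified lists to be sound, do not follow from the documents.

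**What to change.** 1. In the Statistical analysis plan, replace the conditional sentence on RACHS with a commitment: RACHS, collapsed to two levels (for example 1-2 versus 3-6), is a fixed term in every between-arm comparison. For continuous outcomes this means a linear model in place of the plain t-test. If a rank test is used instead, use its version stratified on the same two groups. For logistic models, state that the odds ratio is conditional on RACHS.
2. Reconcile Appendix B with the three randomisation descriptions. Either state that the blocks are generated within the two collapsed RACHS strata, or delete the label. If enrolment has begun on a single list, delete it.
3. In both cases, set the RACHS level from the planned operation before allocation, so that a change in theatre cannot alter it.

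The first change is the one that matters; stratified lists are optional. Six separate strata would be too sparse: 108/6 = 18 children per stratum even if they were evenly spread, with blocks of up to 8.

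The cost is a few lines of wording, plus a second list if stratification is chosen. RACHS is already a baseline item on the Acupuncture Study Documentation Guide, and the sample size stays at 108. One small drawback is that the planned operation will sometimes differ from the one performed.
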